# CONTENTS

# **Table of Contents**

| 1. SYNPOSIS  | 3  |
|--|----|
| 2. BACKGROUND AND RATIONALE  | 4  |
| 2.1. Executive Summary   | 4  |
| 2.2 Relevant Literature and Pilot Data   | 5  |
| 3. AIMS, OBJECTIVES AND HYPOTHESIS   | 8  |
| RO3 - determine the degree to which lactose ingestion alters dietary fat oxidation | 8  |
| 4. PROGRAMME AND METHODOLOGY   | 9  |
| 4.1. Study Design  | 9  |
| 4.2. Primary Outcome   | 9  |
| 4.3. Secondary Outcomes  | 9  |
| 4.4. Tertiary Outcomes   | 9  |
| 4.5. Participants and Eligibility Criteria   | 9  |
| 4.6. Recruitment   | 10 |
| 4.7. Screening   | 11 |
| 4.8. Schedule of Measurements  | 11 |
| 4.9. Measurements and Analysis   | 13 |
| 4.10. Sample Size  |    |
| 4.11. Statistical Analyses   | 14 |
| 4.12. Storage and Management of Data   | 14 |
| 4.13. Expenses and Benefits  | 15 |
| 5. DISADVANTAGES/RISK AND DISCOMFORT   | 15 |
| 6 REFERENCES   | 16 |

| Study Title            | Revealing the mechanisms by which milk sugars exaggerate postprandial lipaemia                               |  |  |  |
|------------------------|--|--|--|--|
| Short Title            | Lactose & Lipids   |  |  |  |
| Trial Design           | Randomised Controlled, Crossover Trial in men and women  |  |  |  |
| Trial Participants     | Men and women aged 18-50 years and premenopausal (for women)   |  |  |  |
| Intervention           | Acute ingestion of three test drinks:  |  |  |  |
|                        | Maltodextrin (Control)   |  |  |  |
|                        | Lactose (Intervention)   |  |  |  |
|                        | Sucrose (Active comparator)  |  |  |  |
| Planned Sample
Size | 24 (12 men and 12 women)   |  |  |  |
| Primary Objective      | To determine to what extent ingestion of lactose exaggerates postprandial triglyceridaemia in men and women. |  |  |  |
| Secondary              | To determine the effect of lactose ingestion on hepatic fatty acid synthesis (de                             |  |  |  |
| Objectives             | novo lipogenesis).   |  |  |  |
|                        | To determine the degree to which lactose ingestion alters dietary fat oxidation.                             |  |  |  |
| Primary                | The effect of lactose versus maltodextrin co-ingestion on postprandial                                |  |  |  |
| Outcomes               | incremental area under the curve (iAUC) for plasma triglyceride concentrations (6-hour postprandial period). |  |  |  |
| Secondary              | The effect of treatment (lactose versus maltodextrin co-ingestion on:  |  |  |  |
| Outcomes               | Postprandial de novo lipogenesis (DNL)   |  |  |  |
|                        | 2) Dietary fat oxidation   |  |  |  |
| -               |  |  |  |  |
| Tertiary               | Treatment (lactose versus fructose versus maltodextrin) by sex (male versus             |  |  |  |
| Outcomes               | female) interaction effect on:   |  |  |  |
|                        | Postprandial incremental area under the curve (iAUC) for plasma  |  |  |  |
|                        | triglyceride concentrations (6-hour postprandial period).  |  |  |  |
|                        | Postprandial de novo lipogenesis (DNL)   |  |  |  |
|                        | 3) Dietary fat oxidation   |  |  |  |
|                        | 4) Postprandial iAUC for plasma insulin concentrations   |  |  |  |
|                        | 5) Postprandial iAUC for plasma glucose concentrations   |  |  |  |
|                        | 6) Postprandial iAUC for plasma galactose concentrations   |  |  |  |
|                        | 7) Postprandial iAUC for plasma fructose concentrations  |  |  |  |
|                        | 8) Postprandial iAUC for plasma VLDL-rich triglyceride [Svedberg flotation                                   |  |  |  |
|                        | rate (S f ): 20-400] concentrations   |  |  |  |
|                        | 9) Postprandial iAUC for plasma chylomicron-rich triglyceride (S f : >400)                        |  |  |  |
|                        | concentrations   |  |  |  |
|                        | 10) Postprandial iAUC for plasma lactate concentrations  |  |  |  |
|                        | 11) Postprandial iAUC for plasma non-esterified fatty acid concentrations                                    |  |  |  |
|                        | 12) Postprandial iAUC for plasma glycerol concentrations   |  |  |  |
|                        | 13) Postprandial iAUC for plasma beta-hydroxybutyrate concentrations   |  |  |  |
|                        | 14) Postprandial iAUC for plasma uric acid concentrations  |  |  |  |
| Funder                 | British Heart Foundation (PG/19/43/34432)  |  |  |  |
| Sponsor                | The University of Bath   |  |  |  |
| Principal              | [name]   |  |  |  |
| Investigator           |  |  |  |  |
| Chief Investigator     | [name]   |  |  |  |

Page IRAS Ref: **271022** Date; 10/03/2021 Version 3.0 3

# 2. BACKGROUND AND RATIONALE

#### 2.1. Executive Summary

Elevated postprandial triglycerides play a causal role in cardiovascular disease (CVD). Restricting sugar intake can reduce circulating triglycerides and nutrition guidelines recommend restricting free sugar intakes for health. Importantly, milk sugars are currently omitted from this restriction simply due to an insufficient evidence-base to draw firm conclusions. Our preliminary data demonstrate that galactose (the unique component of the milk sugar lactose) increases postprandial triglyceride concentrations in lean men, produces a similar metabolic milieu to fructose ingestion, and stimulates triglyceride accumulation in hepatocytes. If galactose exaggerates postprandial triglyceridaemia via common mechanisms to fructose, then this has important health and policy implications due to the potential additive effect of consuming milk products containing free sugars. This project will achieve the following objectives: 1) generate data on the role of lactose in postprandial lipaemia in men and women; 2) establish if hepatic fatty acid synthesis, VLDL availability, and/or changes in handling of dietary fat in the postprandial state are the underlying mechanism(s) by which lactose exaggerates postprandial lipaemia. These data will provide key evidence required to justify longer-term studies, used to refine nutrition guidelines on sugars and CVD. This is timely, as inclusion of milk-based drinks in the Soft Drinks Industry Levy is currently being considered.

[figure not shown]
#### 2.2 Relevant Literature and Pilot Data

Cardiovascular disease (CVD) is a global health burden and postprandial triglycerides play a major causal role in CVD risk. Cardiovascular disease is the leading cause of death worldwide, responsible for ~17 million of the ~54 million deaths in 2013. The total cost of CVD is estimated to rise from \$863 billion in 2010 to \$1044 billion by 2030. With such a huge social and economic burden, prevention is understandably a global priority. Mendelian randomisation suggests a causal role of plasma triglyceride concentrations in coronary heart disease. Furthermore, it is important to consider postprandial triglyceride concentrations (as opposed to post-absorptive) for at least two main reasons. First, in contrast to the fasted state, the fed state captures the total amount of atherogenic lipoproteins in plasma (from both hepatic and intestinal origin); and second, the postprandial state predominates most of the 24-h cycle for the majority of populations in developed countries, thereby better reflecting habitual exposure to atherogenic lipoproteins directly involved in CVD. Individuals with postprandial plasma triglyceride concentrations above 4 mmol×L have a >5-fold increased CVD mortality compared to those with triglyceride concentrations below 1 mmol×L have a riglyceride concentrations and thus, CVD risk.

[figure not shown]
More evidence on the health effects of milk sugars in humans is essential to inform nutrition quidelines. Nutrition is a major determinant of plasma triglycerides and CVD risk. Accordingly, public health authorities (e.g. British Heart Foundation, the Scientific Advisory Committee on Nutrition and the World Health Organisation) provide dietary recommendations for health (6; 7; 8), which consistently advise reducing intakes of free sugars. Indeed, there are metabolic health consequences to the overconsumption of sugars such as fructose; shown to exaggerate postprandial lipaemia and hepatic triglyceride synthesis (i.e. de novo lipogenesis; DNL), whilst suppressing fat oxidation. Importantly, milk sugars are specifically omitted from the current definition of free sugars and thus no upper limit of sugar intake from dairy is provided. This decision is based on "no reported evidence of adverse effects of consumption of intrinsic sugars and sugars naturally present in milk"(7). Whilst this is an appropriate recommendation based on the extent of current evidence available, the statement is based on lack of evidence of an effect, rather than evidence for a lack of an effect. Moreover, sugar intake from dairy products is not negligible, with dairy products contributing more than 20% of total sugar intake in many countries, and more than 95% of the UK population report regularly consuming dairy products. Thus, a better understanding of the health impact of milk sugars should be a priority. The only randomised, controlled study in humans to measure plasma triglycerides in response to galactose supplementation did show that fasting plasma triglyceride concentrations were increased by ~30% with 4 days of galactose supplementation compared to glucose supplementation. In the absence of relevant human data, the best available evidence to date, for the impact of milk sugars on CVD comes from studies on non-human primates. Baboons fed lactose for 17 months displayed almost a 7-fold increase in aortic sudanophilia (reflective of lipid deposition) compared to baboons fed equivalent quantities of sucrose. Furthermore, gross atheromatous lesions were present in ~83% of baboons fed lactose, compared to 33% of baboons fed sucrose. Therefore, it is remarkable that no study has assessed the causal effect of milk sugar in postprandial lipaemia and cardiovascular health in humans.

Galactose ingestion exaggerates postprandial triglyceride concentrations and produces a metabolic milieu indicating similarities to fructose metabolism. Our preliminary data are the first to demonstrate that the addition of galactose to a high-fat meal results in almost a two-fold elevation in postprandial triglyceridaemia compared to glucose ingestion (Figure 1). This demonstrates that ingesting milk sugars increases the exposure of the vascular system to atherogenic lipoproteins. Since the triglyceride response to galactose that we observed appears to be similar in magnitude to that of fructose, we explored whether galactose also reflected fructose

ingestion in other metabolic aspects. Indeed, similar to fructose ingestion, our preliminary data demonstrate that galactose ingestion increases plasma lactate concentrations and lowers plasma alucose and insulin concentrations compared to alucose ingestion (Figure 2). The increase in lactate concentrations with fructose compared to glucose ingestion is due to relatively rapid and unregulated flux of fructose through hepatic metabolic pathways. This results in fructose being rapidly converted into lactate, glucose, hepatic glycogen, and (via de novo lipogenesis) triglycerides. Therefore, the evidence that galactose also increases postprandial plasma lactate concentrations (Figure 2) and enhances hepatic glycogen synthesis, suggests both hepatic galactose metabolism is more similar to fructose than glucose metabolism, and that hepatic de novo lipogenesis may be a contributory factor for the increase in triglyceridaemia. Furthermore, to explore whether hepatocytes are potentially involved in the exaggerated triglyceride response that we observed (as is the case with fructose), we studied intracellular triglyceride accumulation in hepatocytes exposed to glucose alone or combined glucose and galactose at physiologically relevant concentrations for the human liver. The partial replacement of glucose with galactose increased intracellular triglyceride accumulation by ~20% in hepatocytes in vitro (Figure 3). This shows that human liver cells accumulate more lipid when exposed to galactose, which would be expected to have detrimental effects on cardiovascular disease risk in humans, and also implies that the liver could be involved in galactose-induced hypertriglyceridaemia. We therefore hypothesise that galactose ingestion also stimulates hepatic de novo lipogenesis to a greater extent than glucose ingestion.

**Figure 1.** Postprandial triglyceride concentrations following ingestion of milk & cream (0.94 g fat·kg) are exaggerated when co-ingested with additional galactose compared to glucose (both 0.75 g·kg) in lean adults. n = 10. Data are means  $\pm$  SEM. *Unpublished data*.

If lactose exaggerates lipaemia in similar ways to fructose-containing sugars, the public health consequences are substantial. Our preliminary data indicate that galactose ingestion exaggerates postprandial lipaemia via similar mechanisms to fructose ingestion. If galactose and fructose exaggerate lipaemia via common mechanisms, an additive effect would have broad public health implications due to the common co-ingestion of sucrose (glucose-fructose) and milk products containing lactose. Furthermore, developing our understanding of milk sugars is timely, since milk drinks are currently not subject to the Soft Drinks Industry Levy, but former Chancellor of the Excequer, George Osbourne. has recently advocated the inclusion of milk-based drinks in this levy: "I was already, before I left office, looking at whether you could extend it to sugar added to milk products like sugary milkshakes. I think it'll be for others to take further steps forward and I would predict those steps will be taken."(19). Therefore, an additive effect of milk sugars and fructosecontaining sugars on postprandial lipaemia would provide the necessary support for inclusion of milk-based drinks in the sugar levy, and would also inform whether intrinsic milk sugars should contribute to calculation of threshold(s) for the levy. The current thresholds are ≥5 g of free sugar per 100 mL and ≥8 g per 100 mL. If lactose exaggerates lipaemia via common mechanisms to sucrose, then it would be logical to include milk sugars in the calculation of free sugars content for the determination of the levy threshold.

# 3. AIMS, OBJECTIVES AND HYPOTHESIS

**PRIMARY AIM:** To understand the effect and mechanism of lactose on postprandial lipaemia in men and women by addressing the following research objectives (RO):

- RO1 determine to what extent ingestion of lactose exaggerates postprandial triglycridaemia
- RO2 determine the effect of lactose ingestion on hepatic fatty acid synthesis (de novo lipogenesis)
- RO3 determine the degree to which lactose ingestion alters dietary fat oxidation

**HYPOTHESIS:** Lactose co-ingestion with a high-fat meal will exaggerate postprandial lipaemia and stimulate hepatic fatty acid synthesis (*de novo* lipogenesis) to a similar extent to sucrose ingestion, and a greater extent than glucose polymer co-ingestion, whilst suppressing dietary fat oxidation.

#### 4. PROGRAMME AND METHODOLOGY

#### 4.1. Study Design

This research will involve a randomised, double-blind, crossover study that will assess the acute postprandial metabolic responses to three different test drinks. All three test drinks will be comprised of a high-fat milkshake with the addition of either maltodextrin, sucrose or lactose. Individuals will be required to attend the laboratories for a preliminary visit, followed by the three laboratory trial days, with a washout period of 28±7 days.

# 4.2. Primary Outcome

The effect of lactose *versus* maltodextrin co-ingestion on postprandial incremental area under the curve (iAUC) for plasma triglyceride concentrations (6-hour postprandial period).

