### **Pre-trial standardisation**

To assist in producing a similar metabolic state on the morning of laboratory trial days, participants will be asked to record diet and physical activity for 48 h before the first trial, and to replicate these for the 48 h before each subsequent trial. Physical activity levels will be confirmed by objective measures using an Actiheart physical activity monitor (Cambridge Neurotechnology Ltd). This is attached to the chest either using ECG pads or a chest strap for measurement of free-living physical activity.

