### Laboratory trial days

On the evening before trial days, a 5-mL blood sample will be taken (via venepuncture) for analysis of baseline H enrichment of the body water pool. Participants will then consume a standardised meal with 3 g·kg body water  of H2O for the assessment of fasting hepatic DNL. Participants will continue to consume H2O throughout trial days for the measurement of postprandial DNL.

On postprandial study days, participants will arrive at the laboratories in a rested, overnight fasted state, after 24-hours of diet and physical activity standardisation.

Body mass will first be recorded, and then a cannula will be inserted retrograde into a pre-heated dorsal hand vein for arterialised blood sampling, and baseline blood and expired breath samples will be taken for analysis of plasma metabolite and hormone concentrations, plasma tracer enrichments, and indirect calorimetry, respectively. Participants will then consume a high-fat test drink containing 50 g of fat, plus 100 g of either **lactose**, **sucrose or maltodextrin (Table 1)**. The test drink will also contain 200 mg [U-C]palmitate in order to trace the fate of the dietary fat. This quantity of lactose is roughly equivalent to 400 mL of milk and 400 g plain yoghurt, which is very high but not supraphysiological in light of typical UK intakes.

Table 1. Main laboratory trials and drink composition.

| Trial        | Carbohydrate type mixed with fat source (100 g)      | Fat Source
(50 g)                |
|--------------|--|-------------------------------------|
| Maltodextrin | Glucose polymer; a common sugar substitute (control) | 30 g palm oil and
20 g olive oil |
| Lactose      | Galactose-glucose disaccharide (intervention)        | 30 g palm oil and
20 g olive oil |
| Sucrose      | Fructose-glucose disaccharide (active comparator)    | 30 g palm oil and
20 g olive oil |

Low-calorie-sweetened chocolate flavouring will be added to all drinks.

Participants will be advised that dairy products are used in this study and people following a vegan diet may therefore choose not to participate.

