Blood samples will be drawn at 30, 60, 120, 180, 240, 300 and 360 min after ingestion of the test drink and will be centrifuged for plasma collection and determination of metabolite and insulin concentrations (**Figure 4**). A portion of plasma will undergo density gradient ultracentrifugation to obtain the VLDL-rich [Svedberg flotation rate ( $S_f$ ): 20-400] and chylomicron-rich ( $S_f$ : >400) fractions. Expired breath samples will be taken at 60, 120, 180, 240, 300 and 360 min after ingestion for indirect calorimetry (Douglas bag method) and [ $^{13}$ C] appearance in expired CO2 (by isotope ratio mass spectrometry).

[figure not shown]

Figure 4. Schematic of the trial days

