#### Primary analyses

Summary statistics (e.g. iAUC, AUC, peak concentrations) will be analysed by one-way ANOVA. Time-course data will be assessed by a two-way (time x treatment) ANOVA. Paired t-tests will be used for post-hoc comparisons, which will be corrected for multiple comparisons using the Holm-Bonferonni adjustment.

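### Cheap improvement: the primary triglyceride iAUC is analysed without the visit's fasting value as a covariate, so some precision may be lost

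*Combined protocol and SAP*

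**What the plan says.** Section 4.2 makes the primary outcome the effect of lactose versus maltodextrin on "incremental area under the curve (iAUC) for plasma triglyceride concentrations (6-hour postprandial period"). Section 4.11, Primary analyses, states: "Summary statistics (e.g. iAUC, AUC, peak concentrations) will be analysed by one-way ANOVA". The pairwise step follows: "Paired t-tests will be used for post-hoc comparisons, which will be corrected for multiple comparisons using the Holm-Bonferonni adjustment". No part of 4.11 names a baseline covariate.

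The fasting value will be available. Under Laboratory trial days (section 4.8), "baseline blood and expired breath samples will be taken for analysis of plasma metabolite and hormone concentrations", and the test drink comes afterwards. Then "Blood samples will be drawn at 30, 60, 120, 180, 240, 300 and 360 min after ingestion of the test" drink.

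Two things are not stated: the iAUC formula (net area, or only the area above baseline), and whether the fasting level comes from one draw or from replicates.

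**The concern.** Subtracting the fasting level fixes its slope at exactly 1. That is the best slope only if a difference in measured fasting triglyceride between two visits carries through one-for-one to the postprandial level. Random error in the fasting sample does not carry through, so subtraction adds that error to the endpoint. A model that estimates the slope uses the same data and can do better.

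What is at stake is the precision of the primary contrast. Its validity is not in question: drink order is randomised and the fasting sample precedes the drink, so neither the planned nor the adjusted analysis biases the comparison.

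**Working it through.** **1. The plan's own figure.** Section 4.10 gives d = 0.75, 24 participants, alpha 0.05 and power 0.94. A two-sided paired t-test (noncentral t, 23 df) gives 0.9403, so the figure reproduces.

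**2. Weight of the fasting sample.** Assume net area by the trapezoid rule with one fasting sample. At 0, 30, 60, 120, 180, 240, 300 and 360 min the total-AUC weights are 15, 30, 45, 60, 60, 60, 60 and 30. Subtracting 360 × baseline changes the first weight to 15 - 360 = -345.
- The weights now sum to zero (-345 + 30 + 45 + 4 × 60 + 30 = 0), so a shift that is constant through the visit cancels.
- With equal, independent noise in each sample, the time-0 share of the noise variance is 345² / (345² + 18,225) = 119,025 / 137,250 = 86.7%.

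**3. Noise relative to total variability.** The SD of the paired difference implied by d is 46.51 / 0.75 = 62.0, read as mmol/L·min. This is illustrative only: the pilot compared galactose with glucose over 300 min, and its printed SD of 0.28 does not yield d = 0.75, which is a separate matter. The time-0 sample contributes variance 2 × (345 × s)². For an assumed noise SD s of 0.02, 0.05 or 0.10 mmol/L, that is 2.5%, 15.5% or 61.9% of 62.0².

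**4. Gain from estimating the slope.** Let k be the SD of 360 × the fasting difference divided by the SD of the total-AUC difference, and r their within-person correlation. Then

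variance with covariate / variance of iAUC = (1 - r²) / (1 + k² - 2rk).

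The fitted slope is r/k. The ratio never exceeds 1, and equals 1 when r = k. For k = 1 it reduces to (1 + r)/2. Neither k nor r is in the documents, so these are assumed values:

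| k | r | ratio |
|---|---|---|
| 1 | 0.3 | 0.65 |
| 1 | 0.5 | 0.75 |
| 1 | 0.7 | 0.85 |
| 1 | 0.9 | 0.95 |
| 0.8 | 0.7 | 0.51/0.52 = 0.98 |
| 0.7 | 0.5 | 0.75/0.79 = 0.95 |
| 0.7 | 0.8 | 0.36/0.37 = 0.97 |
| 0.7 | 0.7 | 1.00 |

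**5. Small-sample cost.** The formula ignores the cost of estimating the slope. In simulated three-period crossovers with 24 participants, using all three visits, the SE ratio ran from 0.81 to 0.99 for k = 1. It was about 1.01 at k = r = 0.7, where the true slope is already 1. Null rejection was 0.046 to 0.056. If only the lactose and maltodextrin visits are used, the approximate variance penalty is 22/21, and √(22/21) = 1.024, so the worst case is nearer 2%.

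**6. A physical model.** Assume a fasting shift that persists fully through the visit (between-day SD 0.05 to 0.20 mmol/L), sample noise SD 0.03 to 0.10 mmol/L, and the SD of 62.0 from step 3.
- Variance with the covariate is 0.999 down to 0.505 of the iAUC variance.
- Power moves from 0.940 to between 0.930 and 0.998 after the 22/21 penalty. For noise of 0.05 mmol/L or less it is 0.930 to 0.947.
- Total AUC without a covariate has 0.55 to 3.6 times the iAUC variance.

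**7. The endpoint can stay.** Net iAUC = AUC - 360 × baseline. Once baseline is in the model, only its coefficient differs between the two outcomes (by 360), and the treatment estimate is the same. This does not hold for a positive-only area, which is not linear in the fasting value.

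**The case against.** Unadjusted iAUC is a valid prespecified analysis, and four stronger readings that a reader might infer are not supported.

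- *The plan rests on a single fasting draw.* The documents do not give the number of draws or the formula. Under step 2, duplicate fasting samples would cut the measurement-noise variance to 57% of its single-sample value. The -345 weight is therefore conditional.
- *Day-to-day variation is magnified.* Only noise specific to the fasting sample is. A real shift that lasts the visit is removed, and step 6 shows that subtraction can improve on total AUC. The plan also limits such shifts: "participants will be asked to record diet and physical activity for 48 h before the first trial, and to replicate these" before each later visit. That does not remove assay error.
- *Precision is certainly lost.* The larger gains depend on assumptions such as k = 1. If the postprandial level is the fasting level plus a variable response, and sample noise is small, k below 1 and a slope near 1 are to be expected, and the gain is close to nil.
- *The trial is underpowered.* The 0.94 reproduces, and d comes from pilot iAUC, so baseline noise is already included if that area was computed the same way. A paired t-test at alpha/3 gives 0.85. However, Holm applies that level only to the smallest p-value, section 4.10 invokes closed testing, and none of this concerns the baseline.

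All four limits stand. What they leave is that a pre-drink value already collected goes unused, and that the possible gain from using it outweighs the possible loss.

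**Conclusion.** The point holds as a cheap improvement and not as an error. The primary iAUC forces a slope of 1 on fasting triglyceride, and section 4.11 does not use that value as a covariate, so precision may be lost. The amount cannot be fixed from the documents: error variance would fall by 5% to 35% if k = 1 and r lies between 0.9 and 0.3, and by almost nothing when r is near k. The worst case is an SE about 1% larger when all three visits are modelled together. The -345 min weight assumes net area and one fasting sample. The documents show no bias, no inflated type I error, no mistake in the stated power on this account, and no reason to abandon iAUC.

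**What to change.** Keep iAUC as the primary outcome. In section 4.11:

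1. Prespecify the within-person treatment comparison, fitted to all three visits with participant as a factor, with that visit's fasting triglyceride as a covariate.
2. Report the unadjusted iAUC comparison as a sensitivity analysis.
3. Define iAUC and say which fasting sample or samples form the baseline. State that it is net area if equivalence with covariate-adjusted total AUC is to be claimed.

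The choice should be fixed before unblinding, so that adjustment is not selected on the results. The cost is a few lines of text, one degree of freedom, and an SE up to about 1% larger if the true slope is already 1. No new samples are needed. Whether to add a period term is a separate matter.
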